2.1 Primary Objective

The primary objective of this study is to evaluate potential DDI as measured by the effect of coadministration of 4 separate phosphate binders on the PK of orally administered TPOXX in healthy adult subjects.

2.2 Secondary Objective

The secondary objective of this study is to evaluate the safety and tolerability of 600 mg oral TPOXX administered with 4 different phosphate binders in healthy adult subjects.

3. Study Design

This is a postmarketing, open-label, 5-period crossover drug interaction study designed to evaluate the potential effects of coadministration of 4 different phosphate binders on the PK of orally administered TPOXX in healthy adult subjects. A total of 44 subjects, ages 18 to 50, inclusive, will be enrolled and randomly assigned to 1 of 4 treatment sequences. The study will consist of a screening period (Day –28 to Day –2), 5 treatment periods (Day –1 to Day 31), an end-of-study visit (Day 36 [+2 days]), and a follow-up telephone call (Day 59 [+4 days]). The treatment sequences and periods will be as follows:

Treatment	Period 1	Period 2	Period 3	Period 4	Period 5
Sequence	Treatment	Treatment	Treatment	Treatment	Treatment
ABCDE	A	В	С	D	Е
ACEBD	A	С	Е	В	D
ADBEC	A	D	В	Е	С
AEDCB	A	Е	D	С	В

Draft Statistical Analysis Plan, Version **2.0**Date Issued: 8OCT2022

SIGA Technologies, Inc. Protocol: SIGA-246-023

- Treatment A: A single oral dose of 600 mg (3×200 mg capsules) TPOXX.
- Treatment B: A single oral dose of 600 mg (3 × 200 mg capsules) TPOXX coadministered with a single oral dose of 1600 mg (2 × 800 mg tablets) sevelamer carbonate (Renvela® or generic equivalent).
- Treatment C: A single oral dose of 600 mg (3 × 200 mg capsules) TPOXX coadministered with a single oral dose of 500 mg sucroferric oxyhydroxide (Velphoro®) chewable tablet.
- TPOXX + Calcium Acetate: A single oral dose of 600 mg (3 × 200 mg capsules) TPOXX coadministered with a single oral dose of 1334 mg (2 × 667 mg capsules) calcium acetate (PhosLo® generic equivalent).
- Treatment E: A single oral dose of 600 mg (3 × 200 mg capsules) TPOXX coadministered with a single oral dose of 500 mg lanthanum carbonate (Fosrenol® or generic equivalent) chewable tablet.

There will be a washout period of 7 days between dosing in each treatment period. All subjects will be provided a meal (consisting of approximately 600 calories and 25 g fat). The meal should be completed within 30 minutes. Subjects should be administered study drug as soon as possible following completion of the meal but no more than 30 minutes should elapse between meal completion and study drug administration. Study drug and meals must be taken with water only, and no other beverage except water should be ingested within 3 hours before or 3 hours after study drug administration. Water is allowed at all times throughout the study. Subjects must refrain from taking food for 2 hours after taking study drug as further food consumption may affect drug absorption.

In each period, subjects will report to the study site on Day –1 and remain confined to the study site until 48 hours after dosing in Period 5 (Day 31). Subjects will be monitored for safety and tolerability. Serial blood samples for PK analysis of TPOXX will be collected before dosing (0 hour) and up to 48 hours after administration of the study drug(s).

All subjects will have a follow-up telephone call 30 days after administration of the last dose of study drug (Day 59 [+4 days]) to report any serious adverse events (SAEs). At the time of discharge from the clinical research unit, subjects will be instructed to notify the investigator of any SAEs that occur within 30 days after administration of the last dose of study drug. Serious AEs will be followed until the SAE is stable or until resolution as determined by the investigator and/or medical monitor.

The total duration of the study for each subject, including the screening period, treatment period, the Day 36 (+2 days) end-of-study visit, and the Day 59 (+4 days) follow-up telephone call, will be approximately 87 days.

Schedules of assessments can be found in Section 13.

4. General Statistical Considerations

All statistical analyses will be conducted using statistical analysis system SAS® Version 9.4 (SAS Institute, Cary, NC).

Descriptive statistics for continuous variables will include number of subjects, mean, standard deviation (SD), median, minimum, and maximum, unless otherwise noted. For categorical variables, frequencies and percentages will be presented.

General study descriptors, as in subject disposition, demographics, protocol deviations, and enrollment characteristics, will be summarized for all randomized subjects, regardless of treatment sequence. Otherwise, safety outcomes, as in adverse events, lab values, vital signs, and electrocardiogram measures, will be summarized by treatment. The treatments below will be used for such presentation:

- TPOXX
- TPOXX + Sevelamer Carbonate
- TPOXX + Sucroferric Oxyhydroxide
- TPOXX + Calcium Acetate
- TPOXX + Lanthanum Carbonate

All data listings will be sorted by treatment and subject number.

No algorithm for imputation of missing data will be employed. Missing data will be treated as missing. If partial data exists for concomitant medications, the start dates will be imputed to the first of the month (for missing day) or first of the year (for missing day and month) for purposes of assigning a prior mediation flag.

There are no plans to derive visit windows; visits will be used in the analyses as reported on the eCRF.

Study days are calculated with respect to the first dose date as below:

- If the assessment/observation date is on or after the first dose date, then Study Day = Assessment/Observation Date First Dose Date + 1;
- Otherwise, Study Day = Assessment/Observation Date First Dose Date

Baseline will be defined as the day the subject checks in (Day -1) before the first dose of study drug administration, unless otherwise specified.

For summary of safety assessments, if there are repeated measurements at a time point, the first non-missing assessment at that time point will be used in the summary tables.

Unscheduled results will not be included in the summary tables, except for determining Baseline, but will be presented in data listings.

The methodology and data handling specifications for PK data are detailed in Section 8.

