6. STUDY PROCEDURES

Before performing any study procedures, all potential subjects will sign an ICF as outlined in Section 9.3.2.3. Subjects will undergo study procedures at the time points specified in the schedule of events (Table 9-1 and Table 9-2).

The total amount of blood collected from each subject over the duration of the study, including any extra assessments that may be required, will not exceed 500 mL.

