7.3.2 Safety Analyses

Adverse events will be coded by preferred term and system organ class using the latest version of the Medical Dictionary for Regulatory Activities and summarized by treatment and overall. All AE data will be presented in a data listing. Treatment-emergent AEs will be summarized by treatment and overall, as well as by severity and relationship to study drug. Serious AEs and AEs leading to discontinuation of study drug will also be presented in the data listings and summarized by treatment and overall.

Actual values and changes from baseline for clinical laboratory test results, vital sign measurements, and 12-lead ECG results will be summarized by treatment at each time point using descriptive statistics (number of subjects, mean, SD, minimum, median, and maximum). Shift tables will be generated for clinical laboratory test results. Physical examination findings will be presented in a data listing.

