- (c) A full physical examination will include, at minimum, assessment of the following body systems: head, ears, eyes, nose, and throat; cardiac (including auscultation of heart); pulmonary (chest) auscultation of lungs; abdomen; skin; musculoskeletal system; lymphatic system; and neurologic system (cranial nerves, sensation, motor function, coordination, reflexes, and mental status). Symptom-directed physical examination will include an assessment of the heart, lungs, abdomen, a neurologic review, and a review of symptoms for assessment and/or follow-up of reported or potential adverse events.
- (d) Vital sign measurements will include systolic and diastolic blood pressures, heart rate, respiratory rate, and body temperature. Vital signs will be measured at screening, and in each period, at check-in; within 60 minutes prior to dosing; and at 4, 8, 12, 24, and 48 hours following dosing in each period after the subject has been in a seated position for at least 5 minutes.
- (e) Fasting lipid panel will include cholesterol (total, high-density lipoprotein, calculated low-density lipoprotein, and triglycerides).
- (f) Clinical laboratory testing will include hematology and serum chemistry.
- (g) Clinical laboratory testing at screening will include hematology, serum chemistry, and urinalysis.
- (h) For postmenopausal women, a serum follicle-stimulating hormone test will be performed at screening.
- (i) Women of childbearing potential only.
- (includes alcohol, cotinine, amphetamines (including methamphetamines and ecstasy/methylenedioxymethamphetamine), barbiturates, benzodiazepines, cannabinoids (including tetrahydrocannabinol), cocaine metabolites, and opiates (including heroin, codeine, and oxycodone). A urine drug screen including alcohol and cotinine will be collected and sent to the central laboratory at the screening visit. A urine drug screen and alcohol breath test using a breathalyzer will be performed and read locally on Day –1.
- (k) Randomization will occur according to the randomization schedule before study drug administration on Day 1 of Period 1 after it has been confirmed that the subject fulfills all eligibility criteria. Subjects will be randomly assigned to receive study drug in 1 of 4 treatment sequences (ABCDE, ACEBD, ADBEC, and AEDCB) in 1:1:1:1 ratio.

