All clinical laboratory test results will be presented in the data listings. Laboratory values that are outside of the normal reference range will be flagged in the data listings.

Actual results and change from baseline for hematology, serum chemistry and urinalysis at each time point will be summarized for the safety population. Shift from baseline in terms of low/normal/high for hematology and serum chemistry tests, and in terms of normal/abnormal for urinalysis tests will be summarized for the safety population. Abnormal laboratory values for hematology, serum chemistry and urinalysis, defined as any laboratory value with a toxicity grade of 1 or above, will be presented in a listing.

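### One pre-study baseline for all five crossover treatments confounds the TPOXX-alone versus binder comparison of laboratory and vital-sign changes and shifts with time in study

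*Combined protocol and SAP*

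**What the plan says.** SAP Section 4 (General Statistical Considerations) states: "Baseline will be defined as the day the subject checks in (Day -1) before the first dose of study drug administration". The sentence closes with a qualifier that leaves room for a different definition elsewhere, but it is never used: SAP 9.2 (laboratory), 9.3 (vital signs) and 9.5 (ECG) name no other baseline. The schedule of events has one admission, on Day -1, followed by confinement to Day 31.

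The summaries are by treatment. SAP Section 4: "Otherwise, safety outcomes, as in adverse events, lab values, vital signs, and electrocardiogram measures, will be summarized by treatment". Protocol 7.3.2: "Actual values and changes from baseline for clinical laboratory test results, vital sign measurements, and 12-lead ECG results will be summarized by treatment". SAP 9.2 adds: "Actual results and change from baseline for hematology, serum chemistry and urinalysis at each time point will be summarized for the safety population", with shift tables.

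The four sequences (ABCDE, ACEBD, ADBEC, AEDCB) all begin with A, TPOXX alone. Each binder appears once in each of Periods 2, 3, 4 and 5.

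The schedule already provides values before every dose. Hematology and chemistry are drawn on Days -1, 7, 14, 21 and 28, each labelled Day -1 of its period. Vital signs are taken "in each period, at check-in; within 60 minutes prior to dosing; and at 4, 8, 12, 24, and 48 hours following dosing" (Protocol Table 9-1, footnote d). Urinalysis is scheduled only at screening and at the end-of-study visit. ECG has no pre-dose tracing in Periods 2 to 5.

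**The concern.** In a crossover study, a change from baseline by treatment should reflect what happened between a pre-dose value and the response to that dose. With one baseline and A always first, the TPOXX-alone column holds short-interval changes and all four binder columns hold long-interval changes. Anything that moves with time in the unit (diet, confinement, blood sampling) enters the binder columns and is largely absent from the TPOXX-alone column. A shift that arises in one period and persists is counted again under each later treatment. The Day 7, 14, 21 and 28 results, which are pre-dose values for the next binder, become post-baseline results.

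The secondary objective is the safety and tolerability of TPOXX given with each binder, and TPOXX alone is the natural comparator. The stake is a spurious or masked difference from TPOXX alone in the laboratory and vital-sign change tables and the laboratory shift tables.

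**Working it through.** **The plan's own calendar.** Doses 7 days apart fall on Days 1, 8, 15, 22 and 29. Then 36 − 29 = 7 days to the end-of-study visit, 59 − 29 = 30 days to the telephone call, and Day -28 to Day 59 is 28 + 59 = 87 calendar days with no Day 0. All three agree with the protocol. The documents state no baseline-to-assessment interval, so it has to be derived.

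**Elapsed time.** With no Day 0 (SAP Section 4 study-day rule), the time from Day -1 to Day d is d days. The post-dose laboratory draw is on Day 2 of each period: Days 2, 9, 16, 23 and 30.

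**PK blood before that draw.** There are 10 PK samples per period of about 5 mL (Protocol 6.1, 6.1.1), or 50 mL per completed period. PK is drawn last when procedures coincide (Table 9-1, footnote a). Taking the laboratory draw at about 24 hours, 8 samples in the current period precede it (pre-dose to 12 hours), or 40 mL. The total in period p is 50 × (p − 1) + 40 mL.

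| Period | Treatment | Days from study baseline to laboratory draw | PK blood before it (mL) | Days from period baseline | PK blood since period baseline (mL) |
|---|---|---|---|---|---|
| 1 | TPOXX alone | 2 | 40 | 2 | 40 |
| 2 | a binder | 9 | 90 | 2 | 40 |
| 3 | a binder | 16 | 140 | 2 | 40 |
| 4 | a binder | 23 | 190 | 2 | 40 |
| 5 | a binder | 30 | 240 | 2 | 40 |

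Each binder's mean is (9 + 16 + 23 + 30)/4 = 19.5 days and (90 + 140 + 190 + 240)/4 = 165 mL. The excess over TPOXX alone is 17.5 days and 125 mL.

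**Vital signs and ECG.** Vital signs on Days 1 to 3 of a period lie 1 to 3 days from study baseline for TPOXX alone and 8 to 31 days for binders. The 4-hour ECG lies 1 day from it for TPOXX alone and 8, 15, 22 or 29 days for binders.

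**Safety-laboratory blood.** The volume per draw is not stated. Assuming 5 to 15 mL, the total by the post-dose draw, counting the Day -1 draw, is 40 + (5 to 15) = 45 to 55 mL in Period 1. In Period 5, after 9 safety draws, it is 240 + 9 × (5 to 15) = 285 to 375 mL. The protocol's limit is that blood collected "over the duration of the study, including any extra assessments that may be required, will not exceed 500 mL".

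**Illustration for hemoglobin (inputs not in the documents).** Assume hemoglobin 14 g/dL, blood volume 4 to 6 L and red-cell replacement of 0 to 50%. Extra fall = 14 × (1 − exp(−extra mL / blood volume in mL)) × (1 − replacement).

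- Mean binder excess, 125 mL: 14 × (1 − exp(−125/4000)) = 0.43 g/dL at the high end; 14 × (1 − exp(−125/6000)) × 0.5 = 0.14 g/dL at the low end.
- Period 5 excess, 200 mL: by the same formula, 0.68 and 0.23 g/dL.

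**The case against.** A reader might infer that the tables cannot separate a binder effect from time at all. The documents do not support that. Actual values are summarized at each time point, so if the Day 7 to 28 results are shown under the treatment that follows, a within-period mean change can be read by subtraction when data are complete. What cannot be recovered this way is the SD of that change or the individual shifts. The SAP also leaves the column for those pre-dose results unstated, because its attribution rule in 9.1 covers adverse events only.

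A reader might also infer that the effects named in Protocol 1.4.1 (hypercalcemia with calcium acetate, hypotension with sucroferric oxyhydroxide) would be missed. They have other routes. High calcium is graded on absolute cut-offs and any Grade 1 or higher result is listed. Clinically significant changes become adverse events, assigned to the most recent treatment. Blood pressure is also summarized as actual values.

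Nor is the hemoglobin effect established, or confined to binders. TPOXX alone has 40 mL of PK blood against a binder mean of 165 mL, about a quarter. The lower bound depends on capping replacement at 50%; full replacement would give zero. Grade 1 low hemoglobin begins at 10.9 g/dL in men and 10.4 g/dL in women, well below the assumed 14.

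The study baseline has a real merit: it is the only value before any TPOXX dose, and it shows cumulative change. The root cause is the design, with A always first, and no choice of baseline cures that for raw values. Finally, the residual per-period check-in wording could suggest that period baselines were intended. The reference to the first dose and the single admission point the other way, and if period baselines were intended, SAP Section 4 needs to say so.

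These points limit the reach of the concern. They do not remove the unequal intervals in the change and shift tables.

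**Conclusion.** The point holds within limits. For hematology, chemistry and vital signs, the by-treatment changes, and for the laboratory tests the shifts, compare TPOXX alone with each binder over unequal intervals: 2 against 9 to 30 days for the laboratory draw, and 1 to 3 against 8 to 31 days for vital signs, with about 125 mL more PK blood on average before the binder laboratory sample. The day counts rest only on the schedule. The PK volumes also take about 5 mL per sample and a laboratory draw at about 24 hours; placing it after the 24-hour PK sample adds 5 mL to every period and leaves the excess unchanged. The hemoglobin range of 0.14 to 0.43 g/dL is illustrative only.

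Binder-versus-binder comparisons are balanced among completers. Adverse-event tables, grades on absolute thresholds, actual-value summaries and the primary PK analysis do not use this baseline. Safety is a secondary, descriptive objective with no decision rule on these tables. The change is worth making because it is cheap, not because a study conclusion depends on it.

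**What to change.** In SAP Section 4, define a period-specific baseline for the by-treatment change and shift tables:

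- Hematology and chemistry: Day -1 of the same period (Days -1, 7, 14, 21, 28).
- Vital signs: the reading within 60 minutes before dosing in the same period.
- Show these values as the baseline row of the treatment that follows.

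Keep the study baseline for ECG, for Day 36, and for one overall table of cumulative change. State separately that the urinalysis baseline is the screening sample, since no Day -1 urinalysis is scheduled. The SAP appendix grades creatinine and creatinine clearance partly against the participant's own baseline, so say which baseline applies there.

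The cost is SAP wording and table programming; no new sample or visit is needed. With this change every treatment has a 2-day laboratory interval and 40 mL of intervening PK blood. The downsides are that slow cumulative trends then show only in the overall table, raw values remain confounded with period, and ECG changes keep their unequal intervals.

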4.1. Sample Size

The sample size (N = 44 [to allow at least 36 enrolled subjects to complete]) for this study is based on clinical and practical considerations and not on a formal statistical power calculation. The sample size is considered sufficient for the objectives of the study.

Prior estimates of within-subject variability (CVw) of a single dose of 600 mg TPOXX were obtained from Study SIGA-246-018, which evaluated the single-dose PK of TPOXX in a similar population. The CVw% for Cmax, AUC_{0-24} and AUC_{0-inf} ranged from 11.39% to 12.62%, 9.38% to 18.12%, and 15.70% to 18.02%, respectively.

For a sensitivity analysis, a range for CVw of 10%, 15%, and 20% across point estimates of 0.9, 1.0, and 1.1 will be explored. For the sensitivity analysis, assuming a range of CVw, a sample size of 36 evaluable subjects, it is estimated that the precision (ie, half-width of the 90% confidence interval [CI] on the log and ratio scale), and CI with tolerance probability of 80% on

the original scale for each point estimate will be:

				90%
	Half-Width	Half-Width		Confidence
CVw (%)	(log scale)	(original scale)	Point Estimate	Interval
10	0.043	0.044	0.9	(0.862, 0.94)
			1.0	(0.958, 1.044)
			1.1	(1.054, 1.148)
15	0.065	0.067	0.9	(0.843, 0.96)
			1.0	(0.937, 1.067)
			1.1	(1.031, 1.174)
20	0.086	0.090	0.9	(0.826, 0.981)
			1.0	(0.918, 1.09)
l			1.1	(1.009, 1.199)

4.2. Randomization, Stratification, and Blinding

PPD statistician will generate the randomization schedule. Eligible subjects who meet all inclusion and none of the exclusion criteria will be randomly assigned. Randomization numbers will be assigned before the first dose of investigational drug is administered at the Baseline Visit.

Eligible subjects will be randomly assigned to one of the 4 aforementioned sequences in 1:1:1:1 ratio based on the randomization schedule prepared before the study by PPD randomization statistician.

This is an open label study and no stratification will be used.

4.3. Analysis Population

The analysis populations are as follows:

- The PK Population will include subjects who receive at least 1 dose of TPOXX and have sufficient concentration data to support accurate estimation of at least 1 PK parameter.
- The Safety Population will include all subjects who receive any amount of study drug.

5. Subject Disposition

5.1 Disposition

The following will be summarized for the safety population, by treatment sequence and overall for all subjects:

- The number of subjects who received each treatment sequence
- The number of subjects who completed the study
- The number of subjects who did not complete the study (both overall and according to reasons for discontinuation from the study)
- The number of subjects in each analysis population

Subject disposition data will be presented in a data listing.

5.2 Protocol Deviations

Protocol deviations will be collected during monitoring visits. All protocol deviations are to be recorded in CTMS (Clinical Trial Management System) with the indication of whether these are important. These data will be listed including the assignment of not important or important. A *protocol deviation* is any change, divergence, or departure from the study design or procedures defined in the protocol. An *important protocol deviation* (sometimes referred to as a protocol violation or a major protocol deviation) is a subset of protocol deviations that might significantly affect the reliability of the study data or that might significantly affect a subject's safety.

Important protocol deviations will be summarized overall. All protocol deviations will be presented in a data listing, including the categorization of the deviation as important or not important.

